7.6.4 Subject Information

Subject disposition summaries will include the number of enrolled subjects, the number of subjects receiving study drug, the number of subjects completing the study, the number of

subjects withdrawing prematurely, and the reasons for discontinuation. Terminations and premature withdrawals will be summarized by counts and percentages.

Demographics, baseline disease characteristics, prior disease related therapies, and concomitant medications will be summarized using descriptive statistics.

7.6.5 Efficacy Analyses

Clinical response will be based on Investigator assessment and interpretation and used for analysis of efficacy. During the course of the study, the Sponsor may conduct central review of assessments for secondary supportive analyses. All efficacy variables will be defined and analyzed according to IMWG criteria ([Rajkumar et al. 2011](#)), unless otherwise indicated.

7.6.5.1 Efficacy Variables and Analysis (Phase 2)

Objective Response Rate (ORR) defined as the proportion of subjects with a best overall response of sCR, CR, VGPR, or PR, according to IMWG criteria ([Appendix A](#)) as assessed by the Investigator, will be used as the primary analysis for efficacy. The ORR along with a 95% CI, based on the Clopper-Pearson interval will be reported. Secondary analyses of ORR may be repeated in FAS, counting a missing best overall response as a non-responder. ORR will be summarized by each response assessment and best overall response.

Relative reduction in M-protein is defined as the maximum percent reduction from baseline in serum and urine M-protein levels at any time point while on treatment.

Progression-free survival (PFS) is defined as the time from first dose of study drug to first documentation of disease progression or death due to any cause. Subjects who do not experience PD and are alive will be censored at the time of last evaluable tumor assessment. Subjects who do not experience PD and start new anti-cancer therapy will be censored at the last evaluable tumor assessment on or prior to the time of the new anti-cancer therapy. For analyses conducted in the FAS, subjects with no evaluable post-baseline tumor assessments will be censored at the time of receipt of first study drug. Subjects who are lost to follow-up for assessment of PD will be censored at their last evaluable tumor assessment.

Overall Survival (OS) defined as the time from first dose of study drug until date of death due to any cause. Subjects without documentation of death at the time of analysis will be censored as of the date the subject was last known to be alive, or the data cut-off date, whichever is earlier.

PFS and OS will be summarized using Kaplan-Meier estimates.

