7.4.1 Method of Assigning Subjects to Treatment

All subjects will be sequentially assigned a unique identification number during Screening.

Subjects meeting all inclusion and exclusion criteria and completing all screening requirements will be assigned treatment depending on the study enrollment status:

- In Phase 1 of the study, subjects will be sequentially assigned to dose cohorts as specified in the study design ([Section 7.1.1](#)).
- In Phase 2 of the study, subjects will be randomized 1:1 ratio to either the BION-1301 or BION-1301+DEX treatment arm until the BION-1301+DEX arm is filled (n=14); thereafter, all remaining subjects will be assigned to BION-1301 until the arm is filled (n=29 total at selected dose/schedule). If more than one dose level/schedule of BION-1301 is selected for further evaluation in Phase 2, subjects will be randomized in the same fashion.

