7.6 Statistical Analysis

The completeness of the data affects the integrity and accuracy of the final study analysis. Therefore, efforts will be made to ensure complete, accurate and timely data collection, and to avoid missing data. The procedures for handling missing, unused, or spurious data, along with the detailed method for analysis of each variable, transformations, and exploratory analyses will be presented in the Statistical Analysis Plan (SAP); the information below is intended as a guide to planned analyses.

The study is designed in 2 parts: dose escalation (Phase 1) followed by dose-expansion (Phase 2). Phase 1 dose escalation is exploratory in nature and inferential statistics are not the primary focus. Data from the dose escalation and dose expansion components will be summarized separately. There is no intention to compare dose cohorts. In Phase 2, all comparisons will be conducted descriptively.

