7.6.1 Sample Size Determination

During Phase 1, dose escalation will be based on 3+3 guidelines to determine the RP2D and evaluate safety data (including DLTs and TEAEs) and assess the PK-PD of each dose level. The sample size in Phase 1 is predicated on the number of dosing cohorts examined and the number of observed DLTs.

Two treatment arms will be evaluated in Phase 2: BION-1301 monotherapy and BION-1301+DEX.

In Phase 2, a sample size of 29 evaluable subjects in the BION-1301 monotherapy arm achieves 80% power to detect a difference of 9% in ORR using a one-sided exact test with a target significance level of 0.05. The actual significance level achieved by this test is 0.034. The calculation assumes that the population ORR under the null hypothesis is 1% and under the alternative hypothesis is 10%. The sample size includes subjects treated at the corresponding RP2D/schedule during Phase 1 (Dose Escalation).

If more than one dose/schedule is studied in Phase 2, this design will be applied to each RP2D independently.

In Phase 2, a sample size of 14 evaluable subjects in the BION-1301+DEX arm, achieves 80% power to detect a difference of 19% in ORR using a one-sided exact test with a target significance level of 0.05. The actual significance level achieved by this test is 0.008. The calculation assumes that the population ORR under the null hypothesis is 1% and under the alternative hypothesis is 20%.

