7.6.3 Analysis Sets

The following analysis sets will be used for this study:

- ***Evaluable Analysis Set (EAS)***: All subjects who received any amount of study drug and have at least one evaluable post-baseline tumor response assessment or were discontinued due to toxicity. The EAS will be the primary population for analyses of ORR, PFS, DCR, DOR, and relative reduction in M-protein.
- ***Full analysis set (FAS)***: All subjects who receive any amount of study drug. The FAS will be used for analyses of OS, biomarkers, sensitivity analysis of select tumor response-related endpoints, and exploratory endpoints.
- ***Safety population***, defined as all subjects who receive any amount of study drug. All safety analyses will be based on this population. The safety population and FAS are identical.

All analyses of safety, PK, PD, and efficacy data will be performed on all subjects who were enrolled and received at least one dose of study drug.

Additional analysis sets (e.g. evaluable per protocol analysis set) may be defined in the SAP.

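### Does the Phase 2 ORR analysis fail to match its sizing, because Protocol 7.6.5.1 reports only a 95% interval and 7.6 keeps escalation and expansion data apart?

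*Protocol*

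**What the plan says.** **Sizing (Protocol 7.6.1; the synopsis gives the same design).** The monotherapy arm has 29 evaluable subjects, with a null ORR of 1% and an alternative of 10%. This "achieves 80% power to detect a difference of 9% in ORR using a one-sided exact test with a target significance level of 0.05". The section adds: "The actual significance level achieved by this test is 0.034". The BION-1301+DEX arm has 14 evaluable subjects, 1% against 20%, with the same kind of test and target level. There, "The actual significance level achieved by this test is 0.008". No responder threshold is printed for either arm.

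**Analysis (Protocol 7.6.5.1 and 7.6.3).** ORR is the primary efficacy analysis. "The ORR along with a 95% CI, based on the Clopper-Pearson interval will be reported". The section gives no test, null value or success rule. On the population, "The EAS will be the primary population for analyses of ORR, PFS, DCR, DOR, and relative reduction in M-protein". The definition of that set does not refer to study phase.

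**Who is in the 29.** Protocol 7.6.1: "The sample size includes subjects treated at the corresponding RP2D/schedule during Phase 1 (Dose Escalation"). Protocol 7.4.1 agrees: once the combination arm is full, "all remaining subjects will be assigned to BION-1301 until the arm is filled (n=29 total at selected dose/schedule"). The general opening of 7.6 says: "Data from the dose escalation and dose expansion components will be summarized separately". It names no exception.

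**Context.** The same opening of 7.6 describes what follows as a guide, leaves the detailed method for each variable to the SAP, and calls Phase 2 comparisons descriptive. SAP sections 1 and 10 limit the SAP to Phase 1 and drop the Phase 2 analyses. SAP 3.6 records that Phase 2 was not enrolled.

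**The concern.** Two things catch the eye.

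First, the 80% power belongs to a test that the analysis section never mentions. That section offers a 95% interval instead. Read as two-sided, such an interval excludes 1% from below only when the one-sided p-value is at most 0.025, whereas the sizing test works at 0.05. A monotherapy result could therefore reject under the sizing test and still show 1% inside the reported interval. A reader who took the interval as the verdict would be applying a stricter rule with much less power.

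Second, if the separate-summaries sentence in 7.6 applied to ORR, the Phase 2 estimate would rest on fewer than the 29 subjects sized, and the stated 80% would not describe it.

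**Working it through.** **Inputs.** From Protocol 7.6.1: n=29, p0=0.01, p1=0.10; n=14, p0=0.01, p1=0.20; target one-sided level 0.05. From 7.6.5.1: 95% Clopper-Pearson interval. From 7.1.1.1 and 7.1.1.2: Phase 1 cohorts of 3 to 6.

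**Step 1: reproduce the sizing.** For X ~ Binomial(n, p), P(X≥2) = 1 − (1−p)^n − n·p·(1−p)^(n−1).

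- n=29, p=0.01: 1 − 0.7472 − 0.2189 = 0.0340. The neighbouring rules give 0.2528 (1 or more) and 0.0030 (3 or more), so the stated 0.034 identifies 2 or more responders.
- n=29, p=0.10: 1 − 0.0471 − 0.1518 = 0.8011.
- n=14, p=0.01: 1 − 0.8687 − 0.1229 = 0.0084.
- n=14, p=0.20: 1 − 0.0440 − 0.1539 = 0.8021.

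Both stated levels and both stated powers are right. The rule follows from what 7.6.1 prints, although the threshold itself is not printed.

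**Step 2: compare the test with the interval.** The Clopper-Pearson lower limit for x responders is the a-quantile of Beta(x, n−x+1), with a=0.025 for a two-sided 95% interval and a=0.05 for the one-sided 95% bound that matches the test.

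| Result | One-sided p against 1% | Two-sided 95% lower limit | One-sided 95% lower bound |
|---|---|---|---|
| 2/29 | 0.0340 | 0.85% | 1.24% |
| 3/29 | 0.0030 | 2.19% | 2.88% |
| 2/14 | 0.0084 | 1.78% | 2.60% |

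At the planned sizes, test and interval part company only at exactly 2/29. If the true ORR is 10%, that result has probability P(X≥2) − P(X≥3) = 0.8011 − 0.5650 = 0.2361. Using the interval as the success rule would require 3 of 29, with power 56.5%. The BION-1301+DEX arm shows no mismatch.

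**Step 3: the subset reading.** Assume that 3 to 6 of the 29 come from Phase 1 and are left out. Then n is 29−3=26 to 29−6=23, and the same formula gives:

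- n=26, p=0.10: 1 − 0.0646 − 0.1867 = 0.7487.
- n=23, p=0.10: 1 − 0.0886 − 0.2265 = 0.6849.

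The range of 3 to 6 is an assumption from the cohort size, not a bound. Protocol 7.1.1.3 lets other escalation subjects move to the selected dose later, and the documents do not say whether they would count.

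**Step 4: set the passages side by side.** Section 7.6.1 says what the sample size achieves and states the test, the null and the level. Section 7.6.5.1 says what will be reported. It neither excludes that test nor attaches a decision to the interval. On pooling, the synopsis, 7.6.1 and 7.4.1 are specific and agree; the sentence in 7.6 is a general rule about presentation. Separate summaries by study part can stand beside an ORR on the stated 29.

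**The case for a change.** The strongest case for a change runs as follows. ORR is the primary efficacy analysis, so its section should carry the test that justifies the sample size. The mismatch at 2/29 is not remote, since it has probability 23.6% under the design's own alternative. The descriptive wording in 7.6, read with 7.6.2, may concern only comparisons between arms or between dose levels, so it does not clearly replace a single-arm test against 1%. The SAP, which was to supply the detail, does not do so for Phase 2. If estimation alone was intended, 7.6.1 describes a test that is never run.

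Part of this stands. Section 7.6.5.1 would be clearer with a pointer to the test in 7.6.1, and 7.6 with a pointer to the pooling text. The descriptive sentence is too ambiguous to settle the matter. But the SAP's silence is explained by the trial ending before Phase 2. The 23.6% is the chance that a reader who invents a rule from the interval would disagree with the stated test, not the chance that the plan contradicts itself. A design can properly be sized on an exact test and reported as an estimate with a conventional 95% interval. An analyst who wanted the test would find everything needed in 7.6.1.

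**Conclusion.** No change follows. This is detail that an analyst would fill correctly from the protocol itself, and filling it in the text would gain nothing for this trial.

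The sizing figures are correct. The numerical disagreement is confined to 2 of 29 in the monotherapy arm (lower limit 0.85% against a null of 1%, test p=0.034), and it bites only if the 95% interval is treated as a success rule, which the protocol does not do. The power range of 74.9% to 68.5% rests on an assumed carry-over of 3 to 6 subjects and on a reading of 7.6 that sets aside three more specific statements.

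Restating the test or adding a cross-reference would leave 80%, 0.034 and 0.008 as they are. With Phase 2 not enrolled and its analyses omitted under SAP section 10, no estimate or conclusion of this trial could move. The point would be worth tidying only if the Phase 2 design were used again. In that case the pooling question would apply to every endpoint analysed on the evaluable set, not to ORR alone.

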7.6.5.2 Exploratory Efficacy Variables and Analysis

Duration of response (DOR) is defined as the time from the first tumor assessment that supports the subject's objective disease response to the time of disease progression or death due to any cause. Subjects who do not experience disease progression or death at the time of analysis will be censored using the same rules as described for PFS. DOR will be summarized using Kaplan-

Meier estimates, including the number of events, number of censored subjects, median and 95% confidence intervals.

Disease control rate (DCR) is defined as the percentage of subjects with sCR, CR, VGPR, PR, or stable disease (SD) per IMWG criteria; or MR per EBMT criteria ([Appendix B](#)). The analysis of DCR will be conducted in the same manner as ORR.

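### Read literally, the FAS rule for PFS censors at first dose subjects who die before any evaluable assessment; the EAS definition separately leaves most of them out, so the death can be a PFS event in neither set

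*Protocol*

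**What the plan says.** Protocol 7.6.5.1 measures PFS from first dose to "first documentation of disease progression or death due to any cause". Nothing in that definition requires a tumor assessment before a death can count. The general censoring rule is confined to the living: "Subjects who do not experience PD and are alive will be censored at the time of last evaluable tumor assessment". The same paragraph then gives a rule for analyses in the FAS, where "subjects with no evaluable post-baseline tumor assessments will be censored at the time of receipt of first study drug". That sentence carries neither a condition of being alive nor an exception for death.

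Protocol 7.6.3 makes the FAS all treated subjects. To enter the EAS, a treated subject must "have at least one evaluable post-baseline tumor response assessment or were discontinued due to toxicity". On which set carries PFS, 7.6.3 has two sentences that do not agree. One reads "The EAS will be the primary population for analyses of ORR, PFS, DCR, DOR, and relative reduction in M-protein"; the other, shortly after, reads "All analyses of safety, PK, PD, and efficacy data will be performed on all subjects who were enrolled and received at least one dose". The FAS is otherwise assigned to OS, biomarkers, exploratory endpoints and sensitivity analyses of selected response-related endpoints.

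Protocol 7.6 states that "the information below is intended as a guide to planned analyses" and leaves detailed methods to the SAP. The SAP is limited to Phase 1 (SAP 1), contains no PFS rule, and drops the Phase 2 endpoints (SAP 10).

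**The concern.** A death soon after starting treatment is the least ambiguous PFS event there is. The protocol's definition counts it, but its FAS censoring sentence, followed word for word, does not. A programmer working from that sentence would give the subject zero follow-up and no event, and the FAS PFS curve would be too high.

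The FAS is also where one would look to see whether leaving non-evaluable subjects out of the EAS had flattered the result. For ORR the FAS can do this, because 7.6.5.1 counts a missing best response there as a non-response. For PFS the literal rule works the other way: it takes out of the FAS the same deaths that the EAS definition has already left out. The two curves would then agree with each other, and the agreement would give false reassurance.

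**Working it through.** **1. The plan's own figures.** The plan gives no PFS figure to reproduce. The arm sizes used below come from the ORR design in 7.6.1, which does reproduce with success at 2 or more responders:
- n = 29, 1% versus 10%: alpha = 1 − 0.99^29 − 29(0.01)(0.99^28) = 0.034; power = 1 − 0.9^29 − 29(0.1)(0.9^28) = 0.801.
- n = 14, 1% versus 20%: alpha = 0.008; power = 0.802.

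These figures concern ORR and are not affected by this point.

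**2. What happens to the subject.** Apply 7.6.3 and the literal text of 7.6.5.1 to a treated subject with no evaluable post-baseline assessment:

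| Subject | PFS in EAS | PFS in FAS, literal rule | OS in FAS |
|---|---|---|---|
| Dies, no toxicity discontinuation | not in the set | censored at first dose | death counted |
| Discontinued for toxicity, then dies | event (the first-dose rule is limited to the FAS) | censored at first dose | death counted |

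In the first row the death is a PFS event in neither set. It is lost from the EAS through the EAS definition and from the FAS through the censoring sentence; these are two separate mechanisms. In the second row the FAS counts fewer deaths than the EAS.

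The conflict between the two 7.6.3 sentences does not rescue the first row. If the EAS governs, the subject is absent. If all treated subjects govern, that set is the FAS and the literal rule applies.

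**3. Size.** Inputs: N = 29 monotherapy and N = 14 BION-1301+DEX (7.4.1, 7.6.1); cycles of 28 days, with the first scheduled post-baseline SPEP/UPEP at Cycle 2 Day 1 (Table 2-1). Assumptions: d such deaths before that visit, with d not given in the documents, and no other event or censoring before it.

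- Deaths counted as events: S(28) = (N − d)/N.
- Literal FAS rule: the d subjects leave the risk set at time 0 without an event, so S(28) = 1.
- After that both curves have the same N − d subjects at risk and the same events, so S_corrected(t) = S_literal(t) × (N − d)/N. The literal curve is too high by the factor N/(N − d).

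With d = 1:
- Monotherapy, 29 treated: S(28) = 28/29 = 96.6% instead of 100%; factor 29/28 = 1.04; a reported 50% becomes 50% × 28/29 = 48.3%, which is 1.7 points lower.
- BION-1301+DEX, 14 treated: S(28) = 13/14 = 92.9% instead of 100%; factor 14/13 = 1.08.

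7.6.1 calls the 29 and 14 evaluable subjects, whereas 7.4.1 uses them as the numbers that fill each arm. If the death comes on top of the evaluable number, day-28 PFS is 29/30 = 96.7% or 14/15 = 93.3%, which is almost the same.

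Larger counts are hypothetical and show only how the formula scales. Among 29 treated, d = 3 gives S(28) = 89.7% and turns a reported 50% into 44.8%; d = 5 gives 82.8% and 41.4%.

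**The case against.** The strongest reply is that the FAS sentence should be read within its paragraph. Death is already defined as an event, general censoring is for the living, and the FAS sentence may only supply a censoring date where no assessment exists to provide one. The neighbouring sentences on new anticancer therapy and on loss to follow-up also omit the condition of being alive, which suggests drafting shorthand. The DOR text in 7.6.5.2 borrows the PFS censoring rules for a group it limits explicitly: "Subjects who do not experience disease progression or death at the time of analysis will be censored". This reading is plausible and may be what was meant. But 7.6.5.1 does not say that the event definition takes precedence, and its more specific instruction points the other way, so two competent programmers could produce different curves.

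It can also be said that the protocol text is only a guide. That is true, but the document it defers to has no PFS rule. The SAP's silence should not be read as endorsing the literal rule either: it covers Phase 1 only and never reached the question.

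A reader might infer that the quoted sentence also distorts an EAS-based PFS. It does not; it applies only to the FAS. The EAS curve loses these deaths because of who is admitted to the EAS, so editing 7.6.5.1 alone would leave an EAS-primary PFS as high as before. Nor are all early deaths lost: one recorded as a toxicity discontinuation is in the EAS and counts there.

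Finally, the group is small. Subjects must be ECOG 0–1 at entry (7.3.1), SPEP/UPEP is scheduled at Cycle 2 Day 1 and at EOT (Table 2-1), and 7.5.2.2.1 asks for prompt testing on clinical deterioration. An FAS analysis of PFS is foreseen but not clearly required. All of this stands and limits the weight of the point.

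**Conclusion.** The point holds as a fault in the protocol's stated rule, at minor severity. Taken literally, the FAS sentence contradicts the PFS definition in its own paragraph. Together with the EAS definition, it allows a death before any evaluable assessment, without a toxicity discontinuation, to be a PFS event in neither analysis. The loss is specific to PFS.

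One such death is the reasonable illustration, and its effect is modest: 1.7 points where a 29-subject monotherapy curve reads 50%, and 7.1 points (100% − 92.9%) at day 28 in the 14-subject arm. Both figures rest on an assumed count and on there being no other early event or censoring.

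Two stronger conclusions are not supported. The multi-death cases are not an expected impact, because the documents give no early-death rate. And no reported result is wrong: Phase 2 comparisons were descriptive (7.6), Phase 2 was not enrolled (SAP 3.6), and its efficacy analyses were omitted (SAP 10).

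**What to change.** In Protocol 7.6.5.1, limit first-dose censoring to subjects who are alive, without progression, and have no evaluable post-baseline assessment. Add that a death without prior documented progression is a PFS event on the date of death, even when no post-baseline assessment exists.

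In Protocol 7.6.3, resolve the conflict for PFS in favour of the existing sentence that places efficacy analyses on all treated subjects. If the EAS is kept as primary for PFS, then at minimum require FAS PFS under the corrected rule to be reported beside it every time, because the EAS would still exclude these deaths.

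The cost is one clause and one sentence in 7.6.5.1 and an edit to 7.6.3. All deaths already go on the eCRF (7.5.2.3), so no new data are needed, and the SAP has no PFS rule to amend. The downside is that PFS may look slightly less favourable.
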